2.2.2. Substudies

In the original study design per protocol, three optional longitudinal substudies were planned to be completed within this study in subsets of consenting participants, as follows:

- An amyloid PET substudy involving assessments of amyloid by PET scan at Screening and at Weeks 78 and 104
- A tau PET substudy involving assessments of tau by PET scan at Screening and at Weeks 78 and 104

For participants of these studies, study-specific procedures were required for provision of baseline PET scans

2.2.3. Study Conduct Following Announcement of Study Termination

On 31 January 2024, Biogen announced the early termination of Study 221AD305. The decision was not related to any safety or efficacy concerns. Enrollment in 221AD305 was halted immediately upon the announcement. At that time, over 1000 participants had been enrolled in the study.

Following early termination of the study, Biogen offered the study participants the option to continue to receive treatment in a blinded fashion until 1 May 2024 to allow study participants and their health care providers sufficient time to plan future treatment decisions.

2.2.4. Procedures for Releasing Treatment Assignments Following Announcement of Study Termination

As described in 221AD305 unblinding plan version 3.4, Biogen also decided to provide the treatment assignment information to the investigators, site staff and study participants in a patient-centric fashion, such that all study participants' treatment assignments are planned to be released to the investigators and designated site staff after the date of last patient last dose and prior to the date of the final database lock. In the event that a study participant is not interested in continuing treatment within the study until 1 May 2024 and decides to request the treatment assignment release prior to the date of last patient last dose, Biogen agreed to release treatment assignment to the corresponding investigator and the designated site staff following such requests. Blinded Biogen/IQVIA study team members will remain blinded and will not have access to the subject treatment assignments until final database lock.

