2.2.5. Changes to Study Execution Following Announcement of Study Termination

1) On 31 January 2024, it was announced that as the study is early terminated, participants enrolled in the study may continue receiving treatment until 01 May 2024. Screening and enrollment would be closed for the study. The participant and care partner, as applicable, should return to the site for a safety follow-up visit 30 days after their last dose. On 16 February 2024, Biogen released a document 221AD305 ENVISION Clarification Letter_16FEB2024_Final Signed, which updated the changes to study execution: Early Termination Visit: assessments and timing (Protocol Section 1.3, Table 2)

Due to the early termination of the study, all participants will be asked to complete this early termination (ET) visit, which, to reduce participant burden, will be limited to assessments related

to participant safety. These assessments are reported in Table 1. Participants should complete this ET visit within 30 days of their last dose of study treatment.

2) Follow-up/End of Study (FU/EOS) Visit: assessments and timing (Protocol Section 1.3, Table 2)

Due to the early termination of the study, all participants are asked to complete their Follow-up/End of Study visit (also referred to as the safety follow-up visit) at 12 weeks (+/- 3 days) after the participant's last dose of study treatment. Participants who wish to withdraw and not receive additional dosing through 01 May 2024 are still encouraged to have a safety follow-up visit 12 weeks from their last dose of study treatment. In addition, similar to the ET visit, the number of assessments that need to be completed is now reduced to lessen participant burden. These assessments are reported below in Table 1. If a participant has had their last dose of study treatment and it has been more than 12 weeks since their last dose and the participant has not had their safety follow-up, then they should complete a safety follow-up visit within 30 days, as defined in Table 1.

3) Substudies (Protocol Section 5.1)

Due to the early termination of the study, all the longitudinal substudies are terminated and samples will no longer be collected for amyloid PET, tau PET, at Weeks 52, 78, and 104/ET.

4) Management of participants who had already discontinued treatment and who were following the visit schedule defined in Table 3 (Protocol Section 1.3, Table 3)

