5.4. Protocol Deviations

Protocol deviations identified during site monitoring will be captured in a Protocol Deviation log and categorized as major or minor deviations based on Protocol Deviation Classification (see Section 9.2). The major protocol deviations will be summarized for FAS participants by treatment groups. Major protocol deviations for all FAS participants will be listed. Major protocol deviations related to coronavirus disease (COVID-19) may also be summarized and listed.

A listing will be generated for subjects with protocol alternations due to COVID-19, based on the data on the protocol alternations due to COVID-19 collected from the COVID-19 Impact log CRF page.

A listing will be generated for subjects whose treatment assignments were released to the investigators and designated site staff prior to the final database lock, with the date of treatment assignment release presented. See Section 2.2.2. for details about this unblinding procedure.

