5.7. Safety Endpoints

5.7.1. Adverse Events

Analysis Methods

AEs will be analyzed based on safety analysis set. All AEs will be analyzed based on the principle of treatment emergence. A treatment-emergent AE is defined as an AE that started or worsened after the start of the first dose of study treatment.

To define treatment emergence for AEs with missing start or stop date or time the following additional criteria will be used:

- If both the start and stop dates for a particular AE are missing, then that AE is considered treatment emergent;
- If the start date for a particular AE is missing and the stop date/time falls after the first dose date/time, then that AE is considered as treatment emergent;
- If the start date for a particular AE was the same as the first dose date, and the start time was missing, then that event is considered treatment emergent.

For AEs with a partial start date, the year/month of the event date will be compared to that of the first dosing date to determine whether the event is treatment emergent.

In general, AEs will be analyzed based on incidence proportion. The incidence proportion (%) is defined as the number of subjects with an event divided by the total number of subjects in the analysis population. In determining incidence proportion, both single occurrence and multiple

occurrences of events will be counted as one incidence in the numerator. In the remainder of this document and in table titles, incidence proportion may be referred to simply as "incidence".

Adverse events are coded using the MedDRA dictionary. This coding system provides more than five levels to classify AEs. In general, AEs will be presented by SOC and PT but other classifications may be used if warranted.

An overall summary of AEs will be provided by treatment group and by treatment group stratified by ApoE status. This will generally include the following numbers and percentages of subjects: with any AE, with any AE by maximum severity, with any related AE (related to study drug as assessed by the investigator), with SAE, with related SAE (related to study drug as assessed by the investigator), with AE leading to drug discontinuation, with AE leading to study withdrawal, and fatal events.

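### Treatment assignments may be released to sites and participants before the 12-week follow-up ends, and the SAP's AE tables make no split at release

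*SAP*

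**What the plan says.** **Release.** SAP 2.2.4 records the decision to "provide the treatment assignment information to the investigators, site staff and study participants in a patient-centric fashion". Under general release, all "treatment assignments are planned to be released to the investigators and designated site staff after the date of last patient last dose", and this is to happen before the final database lock. A participant who does not wish to go on with treatment and "decides to request the treatment assignment release prior to the date of last patient last dose" can have the assignment released sooner. Only the blinded sponsor and CRO team stays blinded until lock. Protocol 7.4 had held the codes back until the study report was final.

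**Continuing data collection.** SAP 2.2.3 let participants "continue to receive treatment in a blinded fashion until 1 May 2024". SAP 2.2.5 then asks for an early termination visit within 30 days of last dose and a follow-up visit "at 12 weeks (+/- 3 days) after the participant's last dose of study treatment". SAP Table 1 keeps AE and SAE recording open throughout.

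**Analysis.** SAP 5.7.1 treats an AE as treatment-emergent if it starts or worsens after first dose, with no end date. Its overall summary includes participants "with any related AE (related to study drug as assessed by the investigator", and AEs by maximum severity. SAP 4.3 puts all data from the whole study into the final analysis. SAP 3.3 defines an on-treatment period ending 28 days after last dose, but the AE section does not use it.

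**Use of the release date.** SAP 5.4, under protocol deviations, plans a listing of participants whose assignment was released before lock, "with the date of treatment assignment release presented". It points to Section 2.2.2 (Substudies) for the procedure, which is in 2.2.4. No table uses the date, and SAP Section 6 does not mention the change in blinding.

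**The concern.** SAP Section 1 makes safety the focus of the final report. Several planned safety outputs rest on site judgement: which complaints are recorded as AEs, how severe they are, whether they are related to study drug, and whether an ARIA event is symptomatic. SAP 5.7.1.6 makes the AE eCRF the primary source for ARIA analysis, so attribution of symptoms passes through the site.

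An investigator who knows the arm may judge the same headache, confusion or fall differently from one who does not, and a participant who knows the arm may report differently. If release precedes the end of follow-up, the AE and related-AE tables combine blinded and unblinded judgements, and a reader of those tables could not tell.

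Release might also affect who stays under observation. Under SAP Table 1, footnote 2, a participant who starts an outside disease-modifying treatment withdraws and has no further visits, and that choice may depend on the arm once it is known. SAP 5.7.1 uses incidence proportions without person-time, so unequal follow-up would not show there.

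**Working it through.** **Inputs**
- First participant dosed 27 July 2022 (SAP 9.1).
- Enrollment halted 31 January 2024; dosing allowed to 1 May 2024 (SAP 2.2.3).
- Follow-up visit 12 weeks = 84 days after last dose (SAP 2.2.5).
- Release date: only a window is given (SAP 2.2.4).
- Assumption: last patient last dose is 1 May 2024.

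**Calendar check.** Week 122 is study day 855. 27 July 2022 + 854 days = 27 November 2024, which agrees with the November 2024 stated in SAP 9.1.

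**Can release fall inside follow-up?** For a last dose on 1 May 2024:
- on-treatment period ends 1 May + 28 days = 29 May;
- early termination visit is due by 1 May + 30 days = 31 May;
- follow-up visit is due 1 May + 84 days = 24 July (window 21 to 27 July).

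The general release window can therefore open up to 84 days before the last follow-up visit. Of these days, 84 − 28 = 56 lie outside the SAP's own on-treatment period. The window closes at database lock. SAP 4.3 places lock after the last participant's last visit, so release after all follow-up is equally allowed.

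**Who is out of reach of general release?** 1 May 2024 − 84 days = 7 February 2024. Participants last dosed by about that date complete 12 weeks before general release can open. Only an early request could unblind them during follow-up.

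**Share of AE observation time after release.** Let T be the days from first dose to a last dose on 1 May 2024, and r the days from last dose to release. The share is (84 − r) / (T + 84) for r up to 84, and 0 after that.

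| First dose | T | T + 84 | r = 0 | r = 28 | r ≥ 84 |
|---|---|---|---|---|---|
| 27 July 2022 (first participant) | 644 | 728 | 84/728 = 11.5% | 56/728 = 7.7% | 0% |
| 31 July 2023 (illustrative) | 275 | 359 | 84/359 = 23.4% | 56/359 = 15.6% | 0% |
| 31 January 2024 (latest enrollee) | 91 | 175 | 84/175 = 48.0% | 56/175 = 32.0% | 0% |

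The last row takes a dose on 1 May. On the nominal 4-weekly schedule, doses fall on 31 January, 28 February, 27 March and 24 April. Follow-up then ends on 24 April + 84 days = 17 July, after 84 + 84 = 168 days. With release on 1 May, 77 days remain, and 77/168 = 45.8%, close to the 48%.

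These are shares of time, not of events. They do not bound the early-request route, because a participant who stops sooner has a smaller T and so a larger possible share.

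**The case against.** **The timing is not established.** This stands. The SAP gives a window, not a date. A reader might infer that sites were in fact unblinded during follow-up for many participants. The documents do not support that: general release could follow the last visit, and the number of early requests is not given. The unblinding plan cited in SAP Section 8 is dated 29 April 2024, two days before the dosing deadline. That is consistent with release soon afterwards but does not prove it.

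**The 48% is an extreme case.** This also stands. It describes one constructed participant and measures time. Protocol 3.3 says most ARIA-E occurs within the first 8 doses, so off-drug time is a poor guide to the share of ARIA events affected.

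**Much of the safety data is protected.** Correct. MRI findings are centrally read (Protocol 5.3.1 and 14.2.5), and SAP 2.2.4 does not name central readers among those who receive assignments. Laboratory and antibody results are objective. Few if any CDR-SB scores should post-date release, because SAP 2.2.5 removes CDR from the early termination and follow-up visits and drops the Week 26, Week 50 and AD-medication visits.

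**The blind was already imperfect.** Investigators review ARIA reports, and Protocol 3.3 gives ARIA-E rates of 35.2% at 10 mg/kg against 2.7% on placebo. A pre-release table is therefore not a perfectly blinded one. But inference from ARIA affects some participants, while formal release is certain knowledge for everyone released.

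**The data are already there.** The SAP 5.4 listing and the AE listing together would let a reader find events with onset after release. They change no summary table. SAP 5.1.1 allows ad hoc analyses, but only as an option after unblinding.

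**Truncated main tables could mislead.** This stands as an argument against replacing the main tables. SAP Section 1 aims to report safety in full, and a cut would move late SAEs and deaths out of the main display.

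**Conclusion.** The point holds as a gap in the plan. The SAP permits release to sites and participants while AEs are still being collected, and no summary separates site-judged data from before and after release. The exposure is limited to AE reporting, symptoms, severity and relatedness.

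Its size cannot be fixed from the documents. For a participant dosed to 1 May 2024, the affected share of AE observation time lies between 0% and about 12% (first participant) or about 48% (latest enrollee). The upper figures assume release at last dose, and the range does not cover early requests. No effect on event counts can be estimated, and any direction of bias is an expectation rather than something the documents show. SAP 5.1.1 plans no statistical testing, so no error rate or power is at stake.

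A reader might go further and conclude that about half of the safety comparison is open-label, or that radiographic ARIA and CDR-SB are compromised. Neither follows: the first turns one extreme share of time into a share of the data, and the second overlooks central reading and the removal of CDR from the remaining visits.

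**What to change.** 1. Keep the all-data tables as the main display.
2. In SAP 5.7.1 and 5.7.1.7, add supplementary tables of AEs, SAEs, related AEs and symptomatic ARIA, restricted to events with onset before each participant's release date.
3. Flag post-release events in the AE listings.
4. Report by arm the number of participants released before their last visit and the time from release to last visit.
5. State in SAP Section 6 that data after release are not blinded at site level, and that severity or causality of earlier events may have been entered or changed after release. A cut on onset date does not remove that second problem.
6. Correct the SAP 5.4 cross-reference from 2.2.2 to 2.2.4.

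No release-date cut of CDR-SB is needed.

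**Cost.** A few extra tables and some SAP wording, using a date already needed for the SAP 5.4 listing. The supplementary tables will hold fewer events. For early requests they are cut at a time the participant chose, which may relate to tolerability, so they should be read beside the full tables and not in their place.

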2.2.5. Changes to Study Execution Following Announcement of Study Termination

1) On 31 January 2024, it was announced that as the study is early terminated, participants enrolled in the study may continue receiving treatment until 01 May 2024. Screening and enrollment would be closed for the study. The participant and care partner, as applicable, should return to the site for a safety follow-up visit 30 days after their last dose. On 16 February 2024, Biogen released a document 221AD305 ENVISION Clarification Letter_16FEB2024_Final Signed, which updated the changes to study execution: Early Termination Visit: assessments and timing (Protocol Section 1.3, Table 2)

Due to the early termination of the study, all participants will be asked to complete this early termination (ET) visit, which, to reduce participant burden, will be limited to assessments related

to participant safety. These assessments are reported in Table 1. Participants should complete this ET visit within 30 days of their last dose of study treatment.

2) Follow-up/End of Study (FU/EOS) Visit: assessments and timing (Protocol Section 1.3, Table 2)

Due to the early termination of the study, all participants are asked to complete their Follow-up/End of Study visit (also referred to as the safety follow-up visit) at 12 weeks (+/- 3 days) after the participant's last dose of study treatment. Participants who wish to withdraw and not receive additional dosing through 01 May 2024 are still encouraged to have a safety follow-up visit 12 weeks from their last dose of study treatment. In addition, similar to the ET visit, the number of assessments that need to be completed is now reduced to lessen participant burden. These assessments are reported below in Table 1. If a participant has had their last dose of study treatment and it has been more than 12 weeks since their last dose and the participant has not had their safety follow-up, then they should complete a safety follow-up visit within 30 days, as defined in Table 1.

3) Substudies (Protocol Section 5.1)

Due to the early termination of the study, all the longitudinal substudies are terminated and samples will no longer be collected for amyloid PET, tau PET, at Weeks 52, 78, and 104/ET.

4) Management of participants who had already discontinued treatment and who were following the visit schedule defined in Table 3 (Protocol Section 1.3, Table 3)

Due to the early termination of the study, participants who discontinued treatment but agreed to remain in the study and follow the abbreviated visit schedule will be asked to complete their ET visit within 30 days and their FU/EOS visit (safety follow-up) visit 12 weeks after their last dose. If they have already had an ET visit following their last dose of treatment, then the ET visit does not need to be repeated. If it has been more than 12 weeks since their last dose and the participant has not had their safety follow-up, then they should complete a safety follow-up visit within 30 days, as defined in Table 1.

5) Visits at Week 26, Week 50, and unscheduled for Change in AD Meds (Protocol Section 1.3, Table 1 and Table 2)

Due to the discontinuation of the Aduhelm program and the early termination of the study, the visits at Week 26, Week 50, and unscheduled for change in AD medication will no longer need to be conducted as only clinical efficacy assessments are collected at these visits.

Table 1 Revised Schedule of Activities for Early Termination Visit and Followup/End of Study Visit for the Terminated ENVISION Study

Study Assessments ¹	Early Termination Visit (within 30 days of last dose)	Follow up/End of Study Visit ^{2,3} (12 weeks after last dose +/- 3 days)
Body Weight	X	X
Urine Pregnancy Test ⁴	X	X

Study Assessments ¹	Early Termination Visit (within 30 days of last dose)	Follow up/End of Study Visit ^{2,3} (12 weeks after last dose +/- 3 days)
Physical Exam	X	X
Neurological Exam	X	X
12-Lead ECG	X	X
Vital Signs ⁵	X	X
Hematology, Blood Chemistry, and Urinalysis	X	X
Anti-Aducanumab Ab	X	X
Coagulation Panel	X X	
Brain MRI ⁶	X X	
C-SSRS-SLV	X X	
Concomitant Therapy and Procedures	Monitor and record continuously throughout the study	
SAE Reporting	Monitor and record continuously throughout the study	
AE Reporting	Monitor and record continuously throughout the study	

¹Clinical efficacy assessments (MMSE, CDR, ADAS-Cog13, ADCS-ADL-MCI, NPI-10, RUD-Lite, QoL-AD) have been removed from the Early Termination Visit and safety follow-up visit to reduce participant burden.

³If it has been more than 12 weeks since the participant's last dose, participants who had discontinued treatment early but had agreed to remain in the study (following the Table 3 Schedule of Activities in the protocol) should complete this Follow-up visit within 30 days of the clarification letter.

⁵Vital signs will include SBP, DBP, heart rate, body temperature, and respiratory rate. Vital signs will be measured with the participant supine and after the participant has been resting for at least 10 minutes. ⁶If an MRI is performed within 14 days of the ET visit, the MRI can be omitted at the ET visit.

2.2.6. Sample Size Considerations

The sample size was mainly based on results from the primary analysis of Study 221AD302. Results from the post-PV4 population (i.e., the 221AD302 and 221AD301 protocol amendment in which the high dose of aducanumab was increased from 6 mg/kg to 10 mg/kg) in pooled data from Studies 221AD302 and 221AD301 were also considered. A total sample size of 1512 participants was planned to have approximately 90% power to detect a mean difference of 0.48 in change from baseline CDR-SB at Week 78 between the 2 treatment groups. This power

²All participants enrolled in the study are to return to the study site at 12 weeks after the last dose of study treatment for Follow up/End of Study visit. The follow-up visit is important and is intended to monitor the participant after a washout period that is based on the drug's half-life. However, if a study participant with their healthcare provider decides to initiate a disease-modifying Alzheimer's treatment outside of the clinical trial prior to completing all mandated protocol study visits, then the participant should withdraw from the study as per protocol (Protocol Section 8.3, Withdrawal of Participants from Study). For these patients when they are withdrawn, no further study visits should be completed.

⁴Pregnancy testing will only be required for women of childbearing potential.

calculation was based on a 2-sided t-test assuming equal variance with a final significance level of 0.05, an SD of 2.33, a dropout rate through Week 78 of 27%, and a randomization ratio of 2:1. The assumed mean difference of 0.48 between the 2 treatment groups represented an approximately 24% reduction in the placebo mean change from baseline at Week 78 if the placebo mean change is estimated to be 2.

In the original study design per protocol, a blinded assessment of the pooled SD for the primary efficacy endpoint may be performed approximately 3 months prior to the completion of enrollment and the sample size may be increased as a result. The sample size could also be increased using internal and external clinical study results that become available after the start of this study. In addition, the sample size may be increased if the dropout rate through Week 78 is estimated to exceed 27%. The sample size will not be reduced based on this assessment.

Following the study early termination decision on 31 January 2024, the blinded assessment of the pooled SD will not be conducted.

3. Definitions

